3.1 Safety Analysis Sets

Safety Set

All subjects who

- have signed an informed consent form, undergone screening procedure(s) and received a subject number,
- received a study vaccination,
- provided post vaccination safety data.

Safety per protocol set

All subjects in the safety Set with the exclusions of the following cases:

- (1) Subjects administered prior to the contract date.
- (2) Subjects who didn't receive MenACWY-CRM.
- (3) Follow-up failure: The subjects whose safety information cannot be identified due to follow-up loss.
- (4) Not applicable to the indication of study drug
[Indication]
- To prevent invasive meningococcal disease caused by Neisseria meningitides serogroups A, C, Y and W-135 in persons 2 months through 55 years of age.
- (5) Subjects who violate of Protocol: Those who do not meet one item at least of the inclusion/exclusion criteria.
[Inclusion criteria]
 - 1) Male and female subjects from 2 months to 55 years of the age at the time of Visit 1 (including all 55 years old subjects, up to one day before their 56th year birthday), who are scheduled to receive vaccination with MenACWY-CRM conjugate vaccine, according to the local prescribing information and routine clinical practice.
 - 2) To whom the nature of the study has been described and the subject or subject's parent/legal representative has provided written informed consent.
 - 3) Whom the investigator believes that the subject can and will comply with the requirements of the protocol.
 - 4) Who are in good health as determined by the outcome of medical history, physical

	CONFIDENTIAL :	Last Update Date
	THIS DOCUMENT AND INFORMATION CONTAINED HEREIN IS PROPRIETARY TO COMPANY AND IS NOT TO BE DISCLOSED WITHOUT THE WRITTEN PERMISSION OF COMPANY.	26-JAN-2016
STATISTICAL ANALYSIS PLAN(V4.0)		

assessment and clinical judgment of the investigator.

[Exclusion criteria]

- 1) Contraindication, special warnings and/or precautions, as evaluated by the investigators, reported in the MenACWY-CRM conjugate vaccine Korean prescribing information
 - 2) Infants who were already enrolled in this trial for previous vaccination.
- (6) Subjects who prescribed off-label dosage:
- Vaccine schedule for children from 2 to 23 months of age :
 - Infants 2 to 6 months of age : Three doses of MenACWY-CRM, each of 0.5 ml, is to be given with an interval of at least 2 months; the fourth dose schedule be administered during the second year of life with an interval of at least 6 months after the third dose.
 - Infants 7 to 23 months of age : MenACWY-CRM is to be administered as two doses, each as single dose (0.5ml), with the second dose administered in the second year of life and at least three months after the first dose.
 - 2 to 55 years of age : MenACWY-CRM is to be administered as a single dose (0.5ml).
- * The infant from 2 to 23 months of age may enroll at any point, in the vaccination series, including those subjects who may already initiated vaccination series. According to parental consents, these subjects may be followed up for 29 days within the surveillance period after subsequent vaccination(s) at the same study site.

Non-Safety per protocol set

Subjects excluded from safety per protocol set except for subjects who did not receive MenACWY-CRM and follow-up failure.

Based on rules for estimation of each number of safety evaluation cases, the following local regulation and Guideline on Standards for re-examination for new drugs, etc of MFDS, non-safety analysis set are excluded from the safety analysis set:

Guideline on Standards for re-examination for new drugs, etc (Chapter II, no. 3)

Patient Population for Surveillance:

- A) Patients planned to receive a drug under surveillance by investigator's medical judgment shall be subject.
- B) Subject who do not use within approved range shall not be included in the subject in principal.

However, if data of subject whose use is beyond approved range is collected, perform analysis as a separate item.

	CONFIDENTIAL :	Last Update Date
	THIS DOCUMENT AND INFORMATION CONTAINED HEREIN IS PROPRIETARY TO COMPANY AND IS NOT TO BE DISCLOSED WITHOUT THE WRITTEN PERMISSION OF COMPANY.	26-JAN-2016
STATISTICAL ANALYSIS PLAN(V4.0)		

C) Describe actual selection methods of subject in detail.

3.2 Efficacy Analysis Set

Not Applicable

4. Endpoints

4.1 Safety Endpoints

Safety will be assessed after administration of study vaccine in terms of the number and percentage of subjects with:

- Local and systemic solicited adverse events reported from study Day 1 (day of vaccination) through study Day 7 post-vaccination;
- Unsolicited AEs reported from study Day 1 (day of vaccination) through study Day 7 post-vaccination;
- Medically attended AEs reported from study Day 1 to study termination (Day 29/early termination);
- SAEs reported from study Day 1 to study termination (Day 29/early termination).

5. Assessment Criteria

5.1 Safety Assessment Criteria

Not Applicable

	CONFIDENTIAL :	Last Update Date
	THIS DOCUMENT AND INFORMATION CONTAINED HEREIN IS PROPRIETARY TO COMPANY AND IS NOT TO BE DISCLOSED WITHOUT THE WRITTEN PERMISSION OF COMPANY.	26-JAN-2016
STATISTICAL ANALYSIS PLAN(V4.0)		

6. Statistical Analyses

6.1 Baseline Characteristics

Descriptive statistics (mean, standard deviation, median, minimum and maximum) for baseline characteristics such as age, height and weight at enrollment will be calculated in the Safety set and Safety per Protocol set.

The following baseline characteristics will be reported:

< Subject Baseline Information >

- gender, age, ethnic origin, children group, weight, height, past diagnosis, kidney disorder, liver disorder, pre-Immunization temperature, temperature location, pregnancy

< Study Vaccine Information >

- vaccine site, number of previous Menveo, study vaccination number, concomitant medications

6.2 Safety Analyses

The number of subjects of AE[†] and the number of AEs[†] incurred shall be calculated, the incidence rate of AEs[†] and its 95% confidence interval will be calculated using the normal approximation on the safety set and safety per protocol set.

† AE : AE includes solicited and unsolicited AE (DAY 1-7), medically attended AE (DAY 1-29) and SAE (DAY 1-29).

6.2.1 Adverse Events by Baseline Characteristics

AE[†]s (as described below) will be reported (n %) for the following baseline characteristics in the safety set and safety per protocol set :

- Age group (2-23 months, 2-10, 11-18, 19-34, 35-55)
- Children group (<18, ≥18)
- Gender (male, female)
- Past diagnosis (yes, no)

	CONFIDENTIAL :	Last Update Date
	THIS DOCUMENT AND INFORMATION CONTAINED HEREIN IS PROPRIETARY TO COMPANY AND IS NOT TO BE DISCLOSED WITHOUT THE WRITTEN PERMISSION OF COMPANY.	26-JAN-2016
STATISTICAL ANALYSIS PLAN(V4.0)		

- Temperature location (axillary, oral, rectal, ear)
- Administration site (left deltoid, right deltoid, left thigh, right thigh, other)
- Concomitant medication (yes, no)
- Kidney disorder (yes, no)
- Liver disorder (yes, no)
- Pregnancy (yes, no)
- Number of previous Menveo (0, 1, 2, 3)
- Study vaccination number (1, 2, 3, 4)

The n(%) of AEs[†] and its 95% confidence interval will be calculated using the normal approximation and analyzed using χ^2 - test. If more than 20% of expected frequencies of the cell counts are less than 5, Fisher's exact test will be used instead of the chi-square test.

[†] AE : AE includes solicited and unsolicited AE (DAY 1-7), medically attended AE (DAY 1-29) and SAE (DAY 1-29).

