3.1 Safety Set

Table 3.1.1 Summary of solicited AE and unsolicited AE for 7 days after vaccination (<6 years)

Safety Set		AE	
		Incidence Rate n (%)	No. of AEs n
Local AE	Local AE		
	Injection site tenderness		
	Injection site erythema		
	Injection site induration		
Systemic AE	Systemic AE		
	Change in eating habits		
	Sleepiness		
	Irritability		
	Vomiting		
	Diarrhea		
	Rash		
	Fever		
UNSOLICITED AE	System Organ Class(SOC)		
	Preferred Term(PT)		
	Sub Total		
Total			

Table 3.1.2 Summary of solicited AE and unsolicited AE for 7 days after vaccination (<6 years)

Safety Set		AE(2-23 months) N=0		AE(2-5years) N=0	
		Incidence Rate n (%)	No. of AEs n	Incidence Rate n (%)	No. of AEs n
Local AE	Local AE				
	Pain				
	Erythema				
	Induration				
Systemic AE	Systemic AE				
	Chills				
	Nausea				
	Malaise				
	Myalgia				
	Arthralgia				
	Headache				
	Rash				
	Fever				
	Sub Total				
UNSOLICITED AE	System Organ Class(SOC)				
	Preferred Term(PT)				
	Sub Total				
Total					

Table 3.1.3 Summary of solicited AE and unsolicited AE for 7 days after vaccination by study vaccination number (2-23months)

Safety Set		1 N=0		2 N=0		3 N=0		4 N=0	
		Incidence Rate	No. of AEs						
		n (%)	n						
Local AE	Local AE								
	Pain								
	Erythema Induration								
Systemic AE	Systemic AE								
	Chills								
	Nausea								
	Malaise								
	Myalgia								
	Arthralgia								
	Headache								
	Rash								
	Fever								
	Sub Total								
UNSOLICITED AE	System Organ Class(SOC)								
	Preferred Term(PT)								

Table 3.1.4 Summary of solicited AE and unsolicited AE for 7 days after vaccination (\geq 6years)

Safety Set		AE	
		Incidence Rate n (%)	No. of AEs n
Local AE	Local AE		
	Pain		
	Erythema		
	Induration		
Systemic AE	Systemic AE		
	Chills		
	Nausea		
	Malaise		
	Myalgia		
	Arthralgia		
	Headache		
	Rash		
	Fever		
UNSOLICITED AE	System Organ Class(SOC)		
	Preferred Term(PT)		
	Sub Total		
Total			

Table 3.1.5 Summary of solicited AE and unsolicited AE for 7 days after vaccination (≥ 6 years)

Safety Set		AE(6-10)		AE(11-18)		AE(19-34)		AE(35-55)		AE(≥ 56)	
		N=0		N=0		N=0		N=0		N=0	
		Incidence Rate (n %)	No of AEs (n)								
Local AE	Local AE										
	Pain Erythema Induration										
Systemic AE	Systemic AE										
	Chills Nausea Malaise Myalgia Arthralgia Headache Rash Fever										
	Sub Total										
UNSOLICITED AE	System Class(SOC)										
	Organ Preferred Term(PT)										
	Sub Total										
Total											

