6.2.1 Adverse Events by Baseline Characteristics

AE[†]s (as described below) will be reported (n %) for the following baseline characteristics in the safety set and safety per protocol set :

- Age group (2-23 months, 2-10, 11-18, 19-34, 35-55, 55-64)
- Children group (<18, ≥18)
- Gender (male, female)
- Past diagnosis (yes, no)

	CONFIDENTIAL :	Last Update Date
	THIS DOCUMENT AND INFORMATION CONTAINED HEREIN IS PROPRIETARY TO COMPANY AND IS NOT TO BE DISCLOSED WITHOUT THE WRITTEN PERMISSION OF COMPANY.	20-APR-2018
STATISTICAL ANALYSIS PLAN(V6.0)		

- Temperature location (axillary, oral, rectal, ear)
- Administration site (left deltoid, right deltoid, left thigh, right thigh, other)
- Concomitant medication (yes, no)
- Kidney disorder (yes, no)
- Liver disorder (yes, no)
- Pregnancy (yes, no)
- Number of previous Menveo (0, 1, 2, 3)
- Study vaccination number (1, 2, 3, 4)

The n(%) of AEs[†] and its 95% confidence interval will be calculated using the normal approximation and analyzed using χ^2 - test. If more than 20% of expected frequencies of the cell counts are less than 5, Fisher’s exact test will be used instead of the chi-square test.

† AE : AE includes solicited and unsolicited AE (DAY 1-7), medically attended AE (DAY 1-29) and SAE (DAY 1-29).

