6.2.3 Analysis of Unsolicited AE

All unsolicited AEs and MAAE recorded in the CRF will be mapped to preferred terms using the most recent MedDRA dictionary and classified by System organ class (SOC) and Preferred Terms (PT). Under the classification standard of MedDRA terms, and all AEs excluding the AEs whose causal relation with the study medication is ‘Not Related’ shall be treated as AEs whose causal relation cannot be excluded {hereafter “Adverse Drug Reaction(ADR)”}.

- ① The frequency and percentage of unsolicited AE (Day 1-7) and MAAE (Day 1-29) according to the expected, serious, severity, frequency, action taken, outcome, relationship to MenACWY-CRM regarding occurred AE will be calculated.
- ② The frequency of unsolicited AEs (Day 1-7) and MAAE (Day 1-29) will be classified into the preferred terms according to the expected, serious, severity, frequency, action taken, outcome, relationship to MenACWY-CRM.
- ③ The number of subjects and percentage of SAE/Serious ADR (SADR), unexpected AE/ADR,

	CONFIDENTIAL :	Last Update Date
	THIS DOCUMENT AND INFORMATION CONTAINED HEREIN IS PROPRIETARY TO COMPANY AND IS NOT TO BE DISCLOSED WITHOUT THE WRITTEN PERMISSION OF COMPANY.	20-APR-2018
STATISTICAL ANALYSIS PLAN(V6.0)		

MAAE/ADR, unsolicited AE/ADR and continuous solicited AE/ADR will be calculated according to the preferred terms. And the number of subjects and percentage by study vaccination number of SAE/Serious ADR (SADR), unexpected AE/ADR, MAAE/ADR, unsolicited AE/ADR and continuous solicited AE/ADR will be calculated according to the preferred terms in infants 2 to 23 months.

- ④ For subjects excluded from safety per protocol set[†], the number of subjects and the percentage of SAE/Serious ADR (SADR), unexpected AE/ADR, MAAE/ADR, unsolicited AE/ADR and continuous solicited AE/ADR will be calculated according to the preferred terms. And the number of subjects and percentage by study vaccination number of SAE/Serious ADR (SADR), unexpected AE/ADR, MAAE/ADR, unsolicited AE/ADR and continuous solicited AE/ADR will be calculated according to the preferred terms in infants 2 to 23 months.

[†] Subject excluded from safety per protocol set: Except for subjects who didn't receive study vaccination and follow-up failure.

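### Infant results pool the four-dose and two-dose schedules in one 2-23-month group, so a schedule or starting-age difference can look like a change with dose

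*SAP*

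**What the plan says.** SAP section 3.1 item (6), the same in V4.0, V5.0 and V6.0, describes two infant schedules:

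- "Infants 2 to 6 months of age : Three doses of MenACWY-CRM, each of 0.5 ml", followed by a fourth dose in the second year of life.
- "Infants 7 to 23 months of age : MenACWY-CRM is to be administered as two doses", the second of them in the second year of life.

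Protocol Amendment 3 (change to section 3.3.2) makes clear that the schedule follows from the age at which the series starts. It also allows infants to enter at any point in the series.

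The analysis sections do not carry this distinction through. Section 6.2.1 of V4.0 and V5.0 has a single infant band ("Age group (2-23 months, 2-10, 11-18, 19-34, 35-55"). V6.0 adds an older group ("Age group (2-23 months, 2-10, 11-18, 19-34, 35-55, 55-64") but leaves the infant band unchanged. The same section breaks adverse events down by "Study vaccination number (1, 2, 3, 4" and by "Number of previous Menveo (0, 1, 2, 3". Section 6.2.3 items 3 and 4 say that the by-dose results "will be calculated according to the preferred terms in infants 2 to 23 months", again as one group. The V4.0 Appendix 1 shells follow suit; one example is "Table 3.1.3 Summary of solicited AE and unsolicited AE for 7 days after vaccination by study vaccination number (2-23months"), which has columns 1 to 4. The disclosure age groups in section 6.3 of V5.0 and V6.0 also keep 2-23 months whole.

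**The concern.** A child on the two-dose schedule has no third or fourth dose. The infants behind dose rows 1 and 2 are therefore a different population from those behind rows 3 and 4, even if nobody drops out. A reader going down the rows will naturally take a change as an effect of repeated dosing, when it may only be the two-dose starters leaving the table. The number of previous doses has the same structure: among on-schedule infants, values 2 and 3 can come only from four-dose starters.

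Two things are at stake. The study monitors use according to the prescribing information, which has two infant schedules, yet the text available plans no rate for the two-dose schedule and isolates the four-dose schedule only in rows 3 and 4. The pooled infant rate also depends on how many infants enrol on each schedule, which the plan neither sets nor asks to be reported.

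**Working it through.** **The plan's own figure.** SAP section 2.2 gives evaluable targets of 3,000 (2-55 years) and 600 (2-23 months), 10% dropout, and 3,960 enrolled. This agrees with (3,000 + 600) x 1.1 = 3,960. Applying the dropout rate directly gives 3,960 x 0.9 = 3,564 evaluable, of whom 660 x 0.9 = 594 are infants, within 1% of the targets. So about 600 infants is the right base. The documents give no adverse event rates by schedule and no schedule mix; both are assumed below.

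**Who can appear in each row, on schedule.**

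| Dose in series | Started at 2-6 months | Started at 7-23 months |
|---|---|---|
| 1 | yes | yes |
| 2 | yes | yes |
| 3 | yes | no |
| 4 | yes | no |

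**Size of the false step.** Let a be the per-dose risk in four-dose starters, b the risk in two-dose starters, both constant over doses (no true dose effect), and m the share of four-dose starters among the infants in rows 1 and 2. Then:

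- rows 1-2 = m x a + (1 - m) x b
- rows 3-4 = a
- step = (1 - m) x (a - b)

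If every scheduled dose is followed, m is simply the share of four-dose starters among infants:

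| a / b | m | Rows 1-2 | Rows 3-4 | Step (points) |
|---|---|---|---|---|
| 60% / 40% | 25% | 45% | 60% | 15 |
| 60% / 40% | 50% | 50% | 60% | 10 |
| 60% / 40% | 75% | 55% | 60% | 5 |
| 50% / 40% | 25% | 42.5% | 50% | 7.5 |
| 50% / 40% | 50% | 45% | 50% | 5 |
| 50% / 40% | 75% | 47.5% | 50% | 2.5 |

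Exchanging a and b gives steps of the same size downward. With a = b the step is zero.

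**If not every dose is followed.** Suppose each infant contributes one dose, spread evenly over its own schedule, and w is the share of four-dose starters among infants. Then m = (w/4) / (w/4 + (1 - w)/2). With a = 40% and b = 30%, w = 20%, 50% and 80% give steps of 8.9, 6.7 and 3.3 points. With all doses followed, the same inputs give 8, 5 and 2. In this case incomplete follow-up makes the step larger.

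**After a split by schedule.** Four-dose starters show a in all four rows and two-dose starters show b in both of theirs. The false step is zero in each stratum.

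**The case against.** The case for leaving the plan alone has real weight. The stated objective is the safety of a single dose, protocol section 7.1 makes all analyses descriptive, and the SAP names no trend or between-dose contrast. The infant sample size is set for one cohort of 600, so reporting that cohort whole follows the design. The rates and shares above are assumptions. All of this stands, and it is why the pooled figure should stay. It does not remove the problem: the plan already produces by-dose infant tables, and their rows are not comparable.

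Several stronger readings are tempting, and the documents do not support them.

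- *Every infant output in the final plan is pooled.* The only infant shells available are those of V4.0. The V5.0 and V6.0 shells, and protocol section 7.6 as amended for infants, cannot be checked. What can be checked is the section text of V4.0 to V6.0.
- *Rows 3 and 4 hold only four-dose starters in every analysis set.* That is true of infants on schedule. The Safety Set and the Non-Safety per protocol set can include off-schedule infants.
- *The rows are doses in the series.* Study vaccination number is not defined and stands beside a separate count of previous doses. If it counts vaccinations within the study, row 1 can hold any series dose. Rows 1-2 still mix schedules and rows 3-4 still exclude on-schedule two-dose starters.
- *The chi-square test by dose has a false-positive rate that can be calculated from this mixing.* The infant by-dose shells carry no p-value. The tested V4.0 table (Table 2.1.14) is not limited to infants, so people aged 2-55 years enter it too. The point concerns misleading estimates.

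**Conclusion.** The point holds in a conditional form. Sections 6.2.1 and 6.2.3 items 3 and 4 of SAP V4.0 to V6.0, with the V4.0 shells, merge two schedules that the SAP itself distinguishes. Among on-schedule infants, this changes the population between by-dose rows 2 and 3. If risk differs by schedule or starting age and both groups enrol, the difference can show up as a change with dose, in either direction. A reader might infer that a false trend will appear; nothing in the documents shows that the risks differ.

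The assumed range of 2.5 to 15 points rests on a risk gap of 10 to 20 points, a four-dose share of 25-75%, no dose effect and full follow-up. No primary hypothesis is affected. The loss is in interpretation: the two-dose schedule has no rate of its own in the text available, and the dose rows cannot be read as a sequence.

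**What to change.** In section 6.2.1, the infant rows of Table 2.1.1 and the infant by-dose tables under section 6.2.3 items 3 and 4:

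- Split infants by schedule at series start (2-6 months; 7-23 months). Age at the study vaccination will not do, because a four-dose starter may receive later doses after 6 months of age.
- Show dose rows within schedule, 1-4 and 1-2, using dose number in the series.
- Keep the pooled 2-23-month figure and state the schedule mix beside it.
- Derive the schedule from birth date and vaccination date when there are no previous doses, and otherwise from the vaccination history needed to apply section 3.1 item (6). Add an unknown-schedule row for infants whose first-dose date was not collected. The data list in protocol section 3.3.1, which predates the infant amendments, has no first-dose date, so availability should be confirmed.

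The cost is extra columns and smaller cells. If 600 infants split 150 and 450, the 95% half-width at a 50% rate, 1.96 x sqrt(0.25/n), is 8.0 and 4.6 points, against 4.0 pooled. The six schedule-by-dose cells will be sparse at preferred-term level. The split removes the schedule mixing but not the rise of age with dose inside the four-dose schedule, whose fourth dose falls in the second year of life. A footnote should say so.

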In case the Diary Card is not retrieved within 10 days after Day 29, subject or subject’s parent/legal representative will be contacted by phone to assess the occurrence of adverse events, determine the subject’s clinical status and complete study termination. All information will be recorded by the site staff on the subject’s medical record and collected in the appropriate section of the CRF.

All SAEs will be monitored until resolution and/or the cause is identified. If a SAE remains unresolved at study termination, a clinical assessment will be made by the investigator and the GSK regional physician to determine whether continued follow up of the SAE is needed.

Table 3.1-1: Safety Assessment Table

Medical History: All significant past diagnoses including all allergies, major surgeries requiring inpatient hospitalization, other significant injuries or hospitalizations, any conditions requiring prescription or chronic medication (i.e., >2 weeks in duration), or other significant medical conditions based on the investigator’s judgment.
	
From birth, collected at clinic visit Day 1

---	--

	CONFIDENTIAL :	Last Update Date
	THIS DOCUMENT AND INFORMATION CONTAINED HEREIN IS PROPRIETARY TO COMPANY AND IS NOT TO BE DISCLOSED WITHOUT THE WRITTEN PERMISSION OF COMPANY.	26-JAN-2016
STATISTICAL ANALYSIS PLAN(V4.0)		

Immediate reactions: Subjects will be assessed for immediate hypersensitivity reactions.	For at least 30 minutes after vaccination
Solicited local adverse events: < 6 years : injection site erythema, injection site induration, injection site tenderness ≥ 6 years : injection site erythema, injection site induration, injection site pain	Days 1-7 after vaccination
Solicited systemic adverse events: < 6 years : change in eating habits, sleepiness, irritability, rash, vomiting, diarrhea, fever ≥ 6 years : chills, nausea, malaise, generalized myalgia, generalized arthralgia, headache, rash, fever	Days 1-7 after vaccination
All unsolicited AEs will be collected	Days 1-7 after vaccination
Medically attended Adverse Events: Events that require a physician's visit or an emergency room visit (events that are managed by telephone or means other than a face-to-face evaluation by a clinician do not qualify as medically attended AEs).	From Day 1 to study termination (Day 29/early termination)
Serious AEs: All SAEs will be collected.	From Day 1 to study termination (Day 29/early termination)

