Male				X ² -test or Exact test
Female				
Total				

Table 2.1.6 Summary of AE by Past diagnosis

Safety Set	No. subjects with AE n (%)	No. AEs n	Total n (%)	p-value
Yes				X ² -test or Exact test
No				
Total				

Table 2.1.7 Summary of AE by Temperature Location

Safety Set	No. subjects with AE n (%)	No. AEs n	Total n (%)	p-value
Axillary				X ² -test or Exact test
Oral				
Rectal				
Ear				
Total				

Table 2.1.8 Summary of AE by Administration Site

Safety Set	No. subjects with AE n (%)	No. AEs n	Total n (%)	p-value
Left Deltoid				X ² -test or Exact test
Right Deltoid				
Left Thigh (Infant only)				
Right Thigh (Infant only)				
Other				
Total				

Table 2.1.9 Summary of AE by Concomitant medication

Safety Set	No. subjects with AE n (%)	No. AEs n	Total n (%)	p-value
Yes				X ² -test or Exact test
No				
Total				

Table 2.1.10 Summary of AE by Kidney Disorder

Safety Set	No. subjects with AE n (%)	No. AEs n	Total n (%)	p-value
Yes				X ² -test or Exact test
No				
Total				

Table 2.1.11 Summary of AE by Liver disorder

Safety Set	No. subjects with AE n (%)	No. AEs n	Total n (%)	p-value
Yes				X ² -test or Exact test
No				
Total				

Table 2.1.12 Summary of AE by Pregnancy

Safety Set	No. subjects with AE n (%)	No. AEs n	Total n (%)	p-value
Yes				X ² -test or Exact test
No				
Total				

Table 2.1.13 Summary of AE by Number of previous MenACWY

Safety Set	No. subjects with AE n (%)	No. AEs n	Total n (%)	p-value
0				X ² -test or Exact test
1				
2				
3				
Total				

Table 2.1.14 Summary of AE by Study vaccination number

Safety Set	No. subjects with AE n (%)	No. AEs n	Total n (%)	p-value
1				

Safety Set	No. subjects with AE n (%)	No. AEs n	Total n (%)	p-value
2				X ² -test or Exact test
3				
4				
Total				

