2.3 Study population

2.3.1 Inclusion criteria

Individuals eligible for enrolment in this study are those:

	CONFIDENTIAL :	Last Update Date
	THIS DOCUMENT AND INFORMATION CONTAINED HEREIN IS PROPRIETARY TO COMPANY AND IS NOT TO BE DISCLOSED WITHOUT THE WRITTEN PERMISSION OF COMPANY.	20-APR-2018
STATISTICAL ANALYSIS PLAN(V6.0)		

1. Male and female subjects from 2 months to 55 years of the age at the time of vaccination (including all 55 years of age subjects, up to one day before their 56th year birthday), who are scheduled to receive vaccination with MenACWY-CRM conjugate vaccine, according to the local prescribing information and routine clinical practice
2. To whom the nature of the study has been described and the subject or subject's parent/legal representative has provided written informed consent (written assent from minors should be also obtained if required by the relevant IRB);
3. Whom the investigator believes that the subject can and will comply with the requirements of the protocol (e.g., completion of the Diary Card);
4. Who are in good health as determined by the outcome of medical history, physical assessment and clinical judgment of the investigator

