7.4 Additional Analyses for DDS (Data Disclosure Shell)

- Frequency and percentage by Age group (2-23 months, 2-10, 11-18, 19-64)
- Frequency and percentage by study termination and reason not completed
- Incidence proportion and the number of Non-SAE
- The number of death resulting from AE (frequency and percentage)
- Incidence proportion and number according to the preferred terms of Non-SAE (frequency and percentage)

7.5 Additional Analyses for AE in the Local Product Label (Unsolicited AE Day 1-29)

- Preferred terms of Serious AE/ADR, unexpected AE/ADR will be presented respectively according to the proportion.

	CONFIDENTIAL :	Last Update Date
	THIS DOCUMENT AND INFORMATION CONTAINED HEREIN IS PROPRIETARY TO COMPANY AND IS NOT TO BE DISCLOSED WITHOUT THE WRITTEN PERMISSION OF COMPANY.	20-APR-2018
STATISTICAL ANALYSIS PLAN(V6.0)		

8. Notes

- Each statistical analysis will be carried out with SAS Software version 9.4 or more recent version.
- In the descriptive statistics, mean, SD, minimum, median, and maximum will be calculated for continuous variables, and frequency and percentage for categorical variables.
- Data including sign of inequality such as “ ≥ 20 ”, “ > 20 ” will be excluded from analysis.
- All test statistics will be the results of two-sided tests with the statistical significant level of 0.05.
- The followings shall be included only in re-examination report:
 - Analysis by type of concomitant medications
 - Item ② of paragraph 6.2.3
 - Estimation of 95% confidence interval for incidence proportion of AEs by background factors
 - Paragraph 6.3, 6.4

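### The adverse-event comparison by past diagnosis is not stratified by age and may be confounded by it

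*SAP*

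**What the plan says.** SAP V6.0, section 6.2.1, compares any-adverse-event incidence across a list of baseline factors that includes "Past diagnosis (yes, no", "Kidney disorder (yes, no" and liver disorder. V4.0 and V5.0 treat these three factors the same way. Each is tested by chi-square, with a switch to Fisher's exact test "If more than 20% of expected frequencies of the cell counts are less than 5". Section 8 (Notes) adds: "All test statistics will be the results of two-sided tests with the statistical significant level of 0.05".

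The Safety Assessment Table in section 2.4 gives the window for medical history, which covers significant past diagnoses, as "From birth, collected at clinic visit Day 1". The SAP does not define the past-diagnosis factor separately; I take it to be this history. Section 2.3.1 admits "Male and female subjects from 2 months to 55 years of the age at the time of vaccination", and also requires subjects "Who are in good health as determined by the outcome of medical history, physical assessment and clinical judgment of the investigator".

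The table shells available are those in V4.0 Appendix 1. "Table 2.1.6 Summary of AE by Past diagnosis" has rows Yes, No and Total, one p-value and no age layer. Age is a separate one-way factor (Tables 2.1.2 and 2.1.3). Protocol section 7.6 asks for safety by age group. No table crosses history with age, and no adjusted or stratified test is planned.

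**The concern.** An infant has had months in which to acquire a diagnosis and an adult has had decades, so a Yes can be expected to become more frequent with age. The outcome also depends on age through the way it is collected. Under 6 years the systemic checklist asks about eating, sleepiness and irritability; from 6 years it asks about chills, malaise and headache. A 15 mm erythema is graded mild in a 5-year-old and absent in a 7-year-old (SAP 6.2.2).

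If both links are real, the crude test partly compares older with younger subjects. A report could then show that people with earlier disease react less, or more, when they do not. It could also miss a real excess among them, which is the worse error in a safety surveillance study.

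**Working it through.** **Plan's own figure.** None is given for this comparison. The SAP plans 3,000 + 600 = 3,600 evaluable subjects, and 3,600 × 1.10 = 3,960 reproduces the planned enrolment. The split into 600 infants and 3,000 older subjects is the only age mix stated.

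**Assumptions (not in the documents).** Five bands: 2-23 months, 2-10, 11-18, 19-34 and 35-55 years, with N = 600, 600, 600, 1,200, 600. Past diagnosis rises steeply (q = 5, 10, 12, 15, 35%) or less steeply (10, 10, 12, 15, 20%). Adverse-event rates r are varied. Past diagnosis has no effect within any band.

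**Formulas.**
- Crude Yes rate = ΣNqr / ΣNq; crude No rate = ΣN(1−q)r / ΣN(1−q).
- With pooled rate p, SE = √[p(1−p)(1/n_Yes + 1/n_No)] and z = difference / SE.
- Rejection probability ≈ Φ(|z|−1.96) + Φ(−|z|−1.96).

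**Worked case: steep q, r = 70, 60, 50, 50, 40%.**
- Yes subjects: 30 + 60 + 72 + 180 + 210 = 552. Events: 21 + 36 + 36 + 90 + 84 = 267. Rate 48.37%.
- No subjects: 570 + 540 + 528 + 1,020 + 390 = 3,048. Events: 399 + 324 + 264 + 510 + 156 = 1,653. Rate 54.23%.
- Difference −5.86 points. With p = 1,920/3,600 = 0.533, SE = 2.31 points and z = −2.54, so the rejection probability is about Φ(0.58) = 72%.

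**Other cases, same formulas.**

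| History gradient | Adverse-event rates by band (%) | Crude difference (points) | Crude test rejects |
|---|---|---|---|
| steep | 70, 60, 50, 50, 40 | −5.9 | 72% |
| steep | 65, 60, 55, 55, 50 | −2.9 | 25% |
| steep | 60, 57, 55, 55, 52 | −1.6 | 10% |
| steep | 40, 45, 50, 50, 60 | +4.2 | 44% |
| less steep | 70, 60, 50, 50, 40 | −2.5 | 17% |
| less steep | 65, 60, 55, 55, 50 | −1.2 | 8% |
| less steep | 60, 57, 55, 55, 52 | −0.6 | 6% |
| either | equal in all bands | 0 | 5% |

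Simulation agrees to within about a point. In every row the Cochran-Mantel-Haenszel test over the five bands rejects in about 5%. A second simulation set, with other age mixes and prevalences of 5% to 30%, gave 4% to 77% for the crude test and 4% to 6% for the stratified one.

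**Masking.** In the worked case, add a true 6-point excess for Yes subjects in every band. Their events become 267 + 0.06 × 552 = 300.1, a rate of 54.37%, so the crude difference is +0.14 points. The crude test detects the excess in 5% of runs and the stratified test in about 72%. With rates of 65, 60, 55, 55, 50% the figures are about 26% and 71%.

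**Kidney and liver disorder.** Assumed prevalences rising with age from 0.1% to 1% give about 13 Yes subjects, and the crude test rejects in 4% to 7%. Prevalences from 0.2% to 3% give 34 to 37 Yes subjects and 5% to 16%. The largest age-induced shifts were 42.3 − 34.7 = 7.6 points and 42.4 − 34.2 = 8.2 points. Sampling error is larger: at a 40% event rate the 95% half-width is 1.96 × √(0.24/13) = 27 points for 13 subjects and 1.96 × √(0.24/37) = 16 points for 37.

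**The case against.** The protocol (section 7.1) calls all analyses descriptive and states no null hypothesis for the primary safety objective. No decision or stopping rule rests on these p-values. That stands and lowers the priority. It does not remove the problem, because the SAP still prescribes tests at 0.05 and a crude percentage difference is confounded with or without a p-value.

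The by-age tables will show whether adverse events vary with age, which is one of the two conditions for confounding. They do not show history by age, so a reader cannot separate the two.

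A reader might infer that the Yes group is older and that the p-values largely reflect age. The documents do not support this. They give no history prevalence by age and no adverse-event rate by age, and the good-health criterion may flatten the history gradient. The table shows that the distortion can be nil, and its sign reverses if adverse events rise with age.

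A reader might also extend the age argument to kidney and liver disorder. With good health required and label precautions excluded, few Yes subjects are likely, and sparse counts matter more there than age.

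Other factors tested crudely, such as administration site and concomitant medication, may vary with age too. They are not assessed here; past diagnosis is singled out because its window is the subject's lifetime.

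**Conclusion.** The past-diagnosis comparison in SAP 6.2.1 may be confounded by age, and nothing else in the plan repairs it. Under assumed values with no true effect, the crude test rejects in about 5% of trials when adverse events do not vary with age, and in about 70% when both gradients are strong. The error may go in either direction, and a real excess of 6 points can disappear. The age-stratified test stays near 5%. Serious distortion requires both history and adverse events to vary clearly with age. That is plausible, but the documents do not establish it. For kidney and liver disorder the concern is sparse data. Free improvement, minor priority.

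**What to change.** In 6.2.1, for past diagnosis:
- Take the reported p-value from a Cochran-Mantel-Haenszel test stratified by non-overlapping age bands: 2-23 months, 2-5, 6-10, 11-18, 19-34 and 35-55 years, with a separate band for anyone older than 55. The V6.0 list has both 35-55 and 55-64, which overlap at 55. Splitting 2-10 at 6 years follows the SAP's own change of checklist.
- Give the age-stratified risk difference with a 95% confidence interval, and print n/N by age band for Yes and No. The crude n (%) may stay as description.

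For kidney and liver disorder, report counts by age band with exact intervals and do not interpret a p-value.

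The cost is a short SAP revision, an age layer in three table shells for each analysis set, and a few lines of SAS. Age is already collected, so no new data are needed.
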